12.2.5 Motor-Behavioral Assessment Scale

The Motor-Behavioral Assessment Scale (Fitzgerald, Jankovic and Percy, 1990) is comprised of three sub-scales:

- I. Behavioral/Social Assessment (16 items): regression of motor skills; regression of communication skills; poor eye/social contact; lack of sustained interest; irritability, crying tantrums; overactive or over-passive; does not reach for objects or people; does not respond to spoken words when addressed by examiners or parents, acts as deaf even to loud noises; feeding difficulties; chewing difficulties; lack of toilet training; masturbation; self-mutilation/pulling hair or ears, scratching, etc.; aggressive behavior; seizures; apparent insensitivity to pain;
- II. Orofacial/Respiratory Assessment (7 items): speech disturbance; bruxism; breath holding; hyperventilation; air-saliva expulsion/drooling; mouthing of hands and objects; biting self and others;
- III. Motor Assessment/Physical Signs (14 items): hand clumsiness; stereotypic hand washing, rubbing, clapping, stroking, kneading; ataxia/apraxia (gait and trunk) or no gait; truncal rocking/shifting weight; oculogyric movements; bradykinesia; dystonia; hypomimia; scoliosis; myoclonus; dyskinesias including chorea/athetosis or oromotor; hypertonia/rigidity; hyperreflexia; vasomotor disturbance.

Each item is rated on a scale from 0 to 4, with '0' indicating normal or never, and '4' indicating very severe or constant. This assessment will be performed at Baseline and at Weeks 8, 16, and 24 during the initial treatment period, and at Weeks 48, 72, 96, 120, 144, 168 and 192 (or at early discontinuation) in the extension treatment period.

12.2.6 Caregiver Top 3 Concerns

The severity of patient symptoms will be assessed using the Caregiver Top 3 Concerns scale, which uses a 100-mm visual analogue scale (VAS). The caregiver will select the 3 symptoms that are most problematic at baseline from a list of 12 possible concerns, and will rate each one using the VAS to indicate the severity on a scale of 0 to 100. The same 3 symptoms will be rated using the VAS at the scheduled visits at Weeks 8, 16, and 24 in the initial treatment period, and Weeks 48, 72, 96, 120, 144, 168 and 192 (or at early discontinuation) in the extension treatment period.

The concerns from which the caregivers will select their top 3 are listed alphabetically below:

- Aggression/frustration (head banging, screaming, spitting)
- Anxiety
- Difficulties with activities of daily living (toileting, feeding, grooming)
- GI problems – constipation, bloating
- Inappropriate social contact/avoids eye to eye contact, etc.
- Involuntary/repetitive/non-purposeful hand movements, hand wringing, mouthing, etc.

Amend. 1, 19Jan2016; Amend. 2, 18May2016; Amend. 3, 21Oct2016; Amend. 4, 03Mar2017; Amend. 5, 29Mar2017; Amend. 6, 13Apr2017; Amend. 7, 02Oct2017; Amend. 8, 02Nov2017; Amend. 9, 11Feb2018; Amend. 10, 29Nov2018; Amend. 13, 10Dec2019; Amendment 14, 17 March 2020, Clean, Final

- Lack of communication
- Lack of hand use
- Motor problems; difficulty with ambulation
- Respiratory difficulties (breath holding - apnea, hyperventilation, air/saliva expulsion/ drooling)
- Seizures
- Self-mutilation.

12.2.7 Rett Syndrome Clinical Severity Scale (RCSS)

The RCSS is a scale specifically designed to assess the severity of symptoms of RTT (Neul et al, 2008). This 13-item measure provides a clinician rating of core symptoms of Rett syndrome on a Likert scale of either 0 to 4 or 0 to 5 with a maximum total score of 58. The Investigator will use the scale to rate the following: frequency and manageability of seizures, respiratory irregularities, scoliosis, ability to walk (gait apraxia), hand use, speech and sleep. A total score, as well as feature-specific scores will be calculated. This scale will be assessed at Baseline and Week 24 (or early discontinuation) in the initial treatment period, and Weeks 48, 72, 96, 120, 144, 168 and 192 (or early discontinuation) in the extension treatment period.

12.2.8 Rater Training

A multicenter Investigators' Meeting will be held to standardize test procedures and consistency of ratings across centers for each of the rating scales, except the CIC and Caregiver Top 3 Concerns, which will be rated by the caregiver.

To ensure the sensitivity and reliability of the assessments, it is requested that the same evaluator at the site conduct the CGI-C, and the same caregiver perform the rating of the Caregiver Top 3 Concerns and CIC, at every visit. It is recognized that it will sometimes not be possible to meet this condition, but every reasonable effort should be made to ensure uniform conditions across evaluations.

13 REPORTING SAFETY INFORMATION

13.1 Adverse Events

Adverse Event evaluations will be performed during the screening period, at baseline and at each visit of the study. Untoward medical events will be collected, from the time of signing of Informed Consent to the end of the safety follow-up period (14 days after last dose of study medication). All Adverse Events will be recorded in the CRF. In addition, all subjects will be followed up for 30 days after their last dose of study medication for the occurrence of any Serious AE.

13.1.1 Glossary

Adverse Drug Reaction (ADR)

In the pre-approval clinical experience with a new medicinal product or its new usages, particularly as the therapeutic dose(s) may not be established, all noxious and unintended responses to a medicinal product related to any dose should be considered adverse drug reactions. The phrase “response to a medicinal product” means that a causal relationship between a medicinal product and an adverse event is at least a reasonable possibility, i.e., the relationship cannot be ruled out.

Adverse Event (AE)

An AE is any untoward medical occurrence in a patient or clinical investigation subject administered a pharmaceutical product and that does not necessarily have a causal relationship with this treatment. An AE can therefore be any unfavorable and unintended sign (including an abnormal laboratory finding), symptom, or disease temporally associated with the use of a medicinal (investigational) product, whether or not related to the medicinal (investigational) product.

Serious Adverse Event (SAE) or Serious Adverse Drug Reaction (Serious ADR)

Any untoward medical occurrence that at any dose:

- Results in death,
- Is life-threatening, i.e., an event which, in the view of the Investigator, places the subject at immediate risk of death from the event as it occurred (it does not include an event which hypothetically might have caused death if it were more severe)
- Requires inpatient hospitalization or prolongation of existing hospitalization,
- Results in persistent or significant disability/incapacity,
- Is a congenital anomaly/birth defect (if exposure to product just before conception or during pregnancy resulted in an adverse outcome in the child), or
- Is an important medical event that may jeopardize the subject or may require medical intervention to prevent one of the outcomes listed above.

Symptoms or medically significant laboratory or instrumental (e.g., electrocardiographic) abnormalities of a pre-existing disease, such as cancer or other disease, should not be considered an adverse event. However, occurrence of new symptoms, or laboratory or instrumental abnormalities, as well as worsening of pre-existing ones, are considered adverse events. Planned procedures that require hospitalization will not be considered SAEs.

Unexpected Adverse Drug Reaction

An Unexpected Adverse Drug Reaction is adverse event, the nature or severity of which is not consistent with the applicable product information (e.g., Investigator's Brochure for an unapproved investigational product or package insert/summary of product characteristics for an approved product).

Non-Serious Adverse Event

A non-serious adverse event is any adverse event that does not meet the criteria listed above for a serious adverse event.

Treatment-Emergent Adverse Events

Adverse events that are newly occurring or worsened in severity after administration of the study medication are considered to be treatment-emergent AEs (TEAEs). In the open-label extension period, only newly occurring AEs and AEs that were ongoing at Week 24 and worsen in severity will be considered TEAEs.

13.1.2 Data Collection

For each event, record the following information on the Adverse Event section of the Case Report Form:

- **Classification of the Event:** Classify the event as either serious or non-serious
- **Description of Signs or Symptoms:** Whenever possible, record a specific diagnosis for the event. If a diagnosis cannot be made, then record each sign or symptom separately, e.g., record nausea and vomiting as two events. If multiple episodes of an event occur, separated by an appropriate time interval to justify considering the subsequent episodes as a repeat occurrence, record each episode separately on the Case Report Form.
- **Onset Date and Time:** Record the date and time the event started. If a change from baseline/previous evaluation in a laboratory test is reported as an adverse event, record the start date as the date of collection of the first lab sample that shows the change.

Stop Date and Time: Record the date and time the event resolved. If a change from baseline/previous evaluation in a laboratory test is reported as an adverse event, record the stop date as the date of collection of the first sample that shows a return to the previous level.

Intensity:

1. **Mild:** Event not resulting in disability/incapacity, which resolves without treatment.
2. **Moderate:** Event not resulting in disability/incapacity, which requires treatment.
3. **Severe:** Event resulting in temporary and mild disability/incapacity, which requires treatment.

Relationship to the Study Agent: Every effort should be made to determine the cause of each adverse event. The correlation between the study agent and the adverse event should be classified as follows:

1. **Probable**
 - a) The event follows a reasonable temporal sequence from administration of the study agent;
 - b) The event follows a known response pattern to the study agent;
 - c) The event cannot be reasonably explained by:
 - the known characteristics of subject's clinical state, or
 - by other therapy administered, or
 - by the diagnostic/interventional procedure;
 - d) There is evidence of partial or complete disappearance of the event after withdrawal of the product (positive de-challenge)

2. **Possible**
 - a) The event follows a reasonable temporal sequence from administration of the study agent;
 - b) Causation of the event by the study agent cannot be excluded;
 - c) The event follows a known response pattern to the study agent but the event could have been produced by:
 - the subject's clinical state, or
 - other therapy administered, or
 - a diagnostic/interventional procedure.

3. **Unlikely**
 - a) The adverse event follows a reasonable temporal sequence from administration of the study agent;
 - b) Other reasons are more likely to be the cause of the adverse event, based on the present knowledge of the
 - disease under treatment, or
 - other therapy administered, or
 - study drug;
 - c) A causal relationship between the adverse event and the study drug can't be ruled out with certainty.

4. **Not Related** The event is either a pre-dose event or is definitely due to causes separate from the administration of the study agent, i.e.,
 - documented pre-existing condition
 - technical and manual procedural problems
 - concomitant medication
 - subject's clinical state.

5. **Unknown** The event does not meet any of the above criteria because of:
 - conflicting data and/or
 - dubious or insufficient/poor evidence
 - the event is not judged as related or not related.

Action Taken in Relation to the Adverse Event:

1. **None**
2. **Drug treatment required** (a medication was prescribed or changed; record on the Concomitant Medication section of the Case Report Form)
3. **Change in dose of concomitant medication**
4. **Non-drug treatment required** (a non-drug treatment was prescribed or changed, record under “Comments” in the Adverse Event section of the Case Report Form)
5. **Hospitalization or prolonged hospitalization**
6. **Diagnostic or clinical test(s) conducted** (attach a copy of the results to the Case Report Form)
7. **Subject discontinued from the study**

Action Taken with the Study Medication:

1. **Study medication dose interruption**
2. **Study medication dose reduction**
3. **Study medication discontinuation**
4. **None**

Subject Outcome:

1. **Recovered without sequelae**
2. **Recovered with sequelae** (describe the sequelae under “Comments” in the Adverse Event section of the Case Report Form)
3. **Not Recovered, event on-going** (follow the subject until a definite outcome can be determined. When follow-up data are collected, report follow-up information under “Comments” in the Adverse Event section of the Case Report Form; if event is serious, fill in a follow-up Serious Adverse Event Report)
4. **Died** (list primary cause of death under “Event Description” of the Adverse Event section of the Case Report Form; if available, attach a copy of the autopsy report to the Case Report Form and send a copy to the Sponsor)

Comments:

Provide other pertinent clinical information and observations under “Comments” in the Adverse Event section of the Case Report Form. For example, record predisposing or contributing conditions, such as previous history, concomitant diseases or medications, and/or procedural risks.

13.1.3 Subject Follow-up

Every attempt should be made to follow the subject until the adverse event has resolved or until the Investigator determines the subject has returned to an acceptable state of health.

13.1.4 Reporting Serious Adverse Events

The Investigator must report **all serious adverse events within 24 hours**, irrespective of the relationship to study medication, to the CRO, automatically through the eCRF or by telephone or fax. The CRO will then forward this information to NEWRON within 24 hours of receipt. The names of the CRO contact will be communicated to the investigators by the CRO prior to the start of subject enrollment.

The minimum information required for an initial report of a Serious AE is as follows:

- Sender of report (name, address of Investigator, site number),
- Subject identification (screening/randomization number),
- Protocol number,
- Reportable event.

In case of death, a comprehensive narrative report of the case should be prepared by the Investigator and sent to the CRO by mail together with the Serious AE Form, retaining a copy on-site. If an autopsy is performed, a copy of the autopsy report should be actively sought by the Investigator and sent to the CRO as soon as available. A copy of the autopsy report will be retained on-site.

A follow-up Serious Adverse Event Report will be completed by the Investigator if important follow-up information (i.e., diagnosis, outcome, causality assessment, results of specific investigations) are made available after submission of the initial form. The follow-up form will be sent to the CRO as described above.

If the Investigator becomes aware of any deaths or serious adverse events after the end of the 30-day follow-up window established in the protocol following investigational product administration, they will be reported to the CRO as described above.

13.1.5 Safety Reporting to Investigators, IRBs, IECs and Regulatory Authorities

The Sponsor or their designee will be responsible for reporting all SAEs to regulatory authorities, investigators, Institutional Review Boards (IRBs) and Independent Ethics Committees (IECs), as applicable, in accordance with national regulations for the United States, Italy, India, the United Kingdom and Australia. For all active investigators located in the United States, the Sponsor or their designee will prepare an expedited report for all SAEs that are unexpected and potentially related to the study drug, and copies will be distributed according to all applicable laws and regulations. The investigational site also will forward a copy of all expedited reports to their IRB.

13.1.6 Reporting of Overdose

If the investigational site staff administering the study medication or the study Pharmacist reports that a subject took more than the requisite number of capsules or a higher dose than was assigned, this will be considered an overdose and must be reported immediately to the Investigator. Any instance of overdose, whether symptomatic or not, must be communicated to the CRO within 24 hours and be fully documented as a Serious Adverse Event. Details of any signs or symptoms and their management should be recorded including details of any antidote(s) administered.

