10.6 Overdosage

To date more than 1800 subjects have been exposed to at least one dose of sarizotan in clinical studies in healthy volunteers and patients with schizophrenia or Parkinson's disease. The maximum single dose given in these studies was 200 mg. This dose, which is 20 times higher than the maximum individual dose to be administered in the current trial, was not associated with any significant adverse effects. Therefore, in case of an accidental overdosage, conservative management of symptoms and signs is advised. The procedure for reporting a symptomatic overdose is described in [Section 13.1.6](#).

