13.1.8 Pregnancy

Females of childbearing potential who are not using a contraception method judged to be adequate by their Health Care Provider, will not be eligible for the study. [*UK only*: Adequate contraception is defined as the use of a hormonal contraceptive or an Intra Uterine Device (IUD), preferably in conjunction with a spermicidal substance. Appropriate guidelines for use of the specific contraceptive should be followed. For patients whose illness is severe, i.e. advanced stage of physical and mental incapacitation, and are sexually inactive, the caregiver and the healthcare provider should discuss the most appropriate option, including abstinence. Adequate contraception should be continued until 4 weeks after stopping study medication.

As a further precaution, a serum pregnancy test will be performed at screening and baseline for all post-pubertal females. In addition, a serum pregnancy test will be performed at Weeks 24, 48, 72, 96, 120, 144, 168 and 192 (or at early discontinuation) for post-pubertal females; additional serum pregnancy tests may be performed, based on local requirements.

If a patient becomes pregnant during the study, she will be discontinued from the study immediately. The Investigator must report all pregnancies, within 24 hours of notification by the patient, to the CRO by email or by fax using the Pregnancy Reporting form. The timelines and other reporting requirements are the same as for a Serious AE. The patient (or her parent or legal guardian/representative) should be instructed to notify the Investigator within 24 hours if it is determined, after completion of the study, that the patient has become pregnant, either during the treatment phase of the study or within 30 days of completing the study. Whenever possible, a pregnancy should be followed to term and for 1 year after delivery of the baby, and any premature terminations reported. The status of the mother and child should be reported to the CRO or NEWRON within 24 hours after delivery, and one year later.

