17.1.5 SERIOUS ADVERSE EVENTS

Serious adverse events (SAEs) are those events recorded as “Serious” on the Adverse Events page of the eCRF. A summary of serious TEAEs by SOC and PT will be prepared.

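### Protocol 13.1.6 makes every overdose a Serious Adverse Event, against the seriousness criteria in 13.1.1, and the SAP carries that classification into the SAE proportion compared between arms

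*Protocol*

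**What the plan says.** Protocol 13.1.6 treats as an overdose any case in which "investigational site staff administering the study medication or the study Pharmacist reports that a subject took more than the requisite number of capsules", or a dose above the one assigned. Any such case, "whether symptomatic or not, must be communicated to the CRO within 24 hours and be fully documented as a Serious Adverse Event".

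Protocol 13.1.1 lists six criteria for a serious event: death, threat to life, hospitalization, disability, congenital anomaly and, as the broadest, an event that "Is an important medical event that may jeopardize the subject or may require medical intervention to prevent one of the outcomes listed above". Overdose is not among them. The same section adds: "A non-serious adverse event is any adverse event that does not meet the criteria listed above for a serious adverse event".

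Protocol 10.6 points to 13.1.6 with the words "The procedure for reporting a symptomatic overdose is described in" that section.

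For analysis, SAP 17.1.5 states that "Serious adverse events (SAEs) are those events recorded as" serious on the eCRF adverse event page, with no exception for overdose. SAP 17.1.1 counts subjects with at least one SAE. Protocol 15.2.5, and the safety analysis paragraph of the synopsis, plan a sarizotan versus placebo comparison of the proportion of subjects with SAEs in the double-blind period.

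**The concern.** The same event can receive two classifications from the same protocol. An extra capsule with no sign or symptom meets none of the six criteria in 13.1.1, and may not even be an adverse event under the definition there. Under 13.1.6 it is nevertheless documented as serious. The SAP takes the recorded flag as it stands, so the conflict passes unfiltered into the headline SAE proportion.

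With about 43 patients per arm, that proportion moves visibly with each patient. If some of the patients behind it had no clinical event, the figure no longer measures what readers of the safety tables, and the Safety Monitoring Board, will take it to measure. A genuine difference in SAEs becomes harder to see.

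**Working it through.** The plan states no figure for overdose or SAE frequency, so there is nothing to reproduce. The check has three parts.

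**1. The sections side by side**

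| Place | Asymptomatic overdose |
|---|---|
| Protocol 13.1.1 | Non-serious unless one of six criteria is met |
| Protocol 13.1.6 | Documented as an SAE in every case |
| Protocol 10.6 | Not mentioned; 13.1.6 is cited for symptomatic overdose |
| SAP 17.1.5 | Counted as an SAE if recorded as serious |
| SAP 17.1.1, Protocol 15.2.5 | Included in the at-least-one-SAE proportion and its comparison |

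One reading would remove the conflict: that 13.1.6 only borrows the SAE reporting timeline. The pregnancy section (13.1.8) shows how the protocol words that intention: "The timelines and other reporting requirements are the same as for a Serious AE". It does not call a pregnancy an SAE. Section 13.1.6 goes further and classifies the event.

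**2. Size per patient**

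Input: about 43 patients per group (Protocol 9.1). A patient whose only SAE is an overdose without clinical consequence adds 1/43 = 2.3 percentage points to that arm. In the pooled sarizotan presentation (SAP section 8) the step is 1/(2 × 43) = 1/86 = 1.2 points. A patient who also has a genuine SAE adds nothing, because subjects are counted once.

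**3. Direction of the effect**

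All rates here are assumptions, since the documents give none. Let p be the true SAE proportion and q the proportion with a recorded overdose that meets no 13.1.1 criterion. Take q as equal in both arms and independent of genuine SAEs. The observed proportion is 1 − (1 − p)(1 − q). With p = 5% on placebo and 20% on high dose, 43 per arm, and power from a two-sided 5% normal-approximation test of two proportions (used only as a yardstick, since the SAP specifies no such test):

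| q | Placebo | High dose | Difference (points) | Risk ratio | Power |
|---|---|---|---|---|---|
| 0% | 5.0% | 20.0% | 15.0 | 4.0 | 56% |
| 2% | 6.9% | 21.6% | 14.7 | 3.1 | 50% |
| 5% | 9.75% | 24.0% | 14.25 | 2.5 | 42% |
| 10% | 14.5% | 28.0% | 13.5 | 1.9 | 33% |
| 20% | 24.0% | 36.0% | 12.0 | 1.5 | 23% |

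For example, at q = 5%: 1 − 0.95 × 0.95 = 9.75% and 1 − 0.80 × 0.95 = 24.0%. The difference shrinks by the factor (1 − q). The risk ratio and the power fall faster because the background rate rises.

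**The case against.** The strongest defence is that a blanket rule is a deliberate safety choice. Sarizotan had not been given to children or to patients with Rett syndrome before (Protocol 7.3), and the stated safety margins are only 1-fold to 5-fold (Protocol 7.1.2). The last criterion in 13.1.1 also leaves room for judgement. This justifies fast notification of every overdose. It does not reconcile the two definitions, because 13.1.6 leaves the investigator no judgement to make.

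The SAP specifies no test on SAEs. Its tables by system organ class and preferred term, and its SAE listing, would show overdoses coded as such. That stands, and it limits the damage to the overall at-least-one-SAE line. The reference in 10.6 is narrower than 13.1.6 and does not strictly contradict it. It still misdescribes the section it cites.

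A reader might infer three stronger conclusions, and the documents support none of them.

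- **That home dosing errors as such enter the SAE comparison.** Nearly all doses are taken at home: of 168 × 2 = 336 double-blind doses, about 4 are given in clinic (Day 1 morning and evening, Day 2 morning, Day 15 morning), leaving 332, or 98.8%. But 13.1.6 opens with "If the investigational site staff administering the study medication or the study Pharmacist reports" and does not name caregivers. A home error enters only if those staff learn of it, for example through drug accountability (Protocol 10.5).
- **That an expected number of such events can be given.** This would need a dosing error rate and a detection rate, and neither document gives either.
- **That the rule could create an apparent SAE difference.** Every arm takes one matching capsule twice daily under blind, so errors should be about equally frequent across arms. A spurious difference would arise only by chance.

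**Conclusion.** The conflict between Protocol 13.1.6 and 13.1.1 is real, and current text carries it into the between-arm SAE proportion. Its size is up to 2.3 points in an arm of 43 for each patient whose only SAE is an overdose without clinical consequence. The total is unknown.

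The likely consequence is dilution. This rests on two assumptions: error rates are similar across blinded arms with matching capsules, and an event documented as an SAE under 13.1.6 is recorded as serious on the eCRF. The power and risk-ratio figures illustrate direction only, because their input rates are assumed.

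The issue does not touch the efficacy analysis, and it loses no safety information. It is worth correcting because the headline SAE figure should have one definition and the correction is small.

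**What to change.** **Protocol.** Reconcile 10.6, 13.1.1 and 13.1.6 so that the classification of an overdose and the seriousness criteria agree and the cross-reference describes the section correctly. Keep the 24-hour notification of every overdose to the CRO. The pregnancy section already shows wording that applies SAE timelines without reclassifying the event.

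**SAP.** Keep the SAE total as recorded in 17.1.1 and 17.1.5. Removing events recorded as serious would make reported and recorded totals disagree. Beside it, add the count and proportion of subjects in each arm with at least one SAE meeting a 13.1.1 criterion, and a separate listing of overdoses by arm. If the eCRF does not capture which criterion was met, assign it in a blinded review before unblinding, as SAP section 5 does for the analysis populations.

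**Cost.** One extra table and one listing, plus a blinded review if it is needed. The protocol wording may need ethics approval if the amendment counts as substantial (Protocol 16.2), across the five countries named in 13.1.5. The SAP describes randomization in the past tense and only the extension as ongoing. The protocol change would therefore mainly serve the extension, and the SAP change is what helps the double-blind comparison.
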